• Requires inpatient hospitalization or prolongation of existing hospitalization Note: Adverse events requiring hospital admissions that are less than 24 hours in duration do not meet this criterion. A scheduled hospitalization for a pre-existing condition that has not worsened during participation in the study does not meet this criterion. Pre-planned hospitalizations for an elective medical/surgical procedure or routine check-ups do not meet this criterion. Admission for CDI relapse will not be included in this definition.

- Results in persistent or significant disability or incapacity
- Results in a congenital anomaly or birth defect

• Results in an important medical event

Note: Important medical events are those that may not be immediately life threatening or result in death or hospitalization but may jeopardize the patient or may require intervention to prevent one of the outcomes listed in the definition above.

3. Planned Hospitalization

A hospitalization planned prior to FMT is to be considered a therapeutic intervention and not the result of a new SAE. If the hospitalization or procedure is executed as planned, it will be recorded in the subject's medical history or procedures. However, if the event/condition worsens during the study, it must be reported as an AE.

4. Adverse reaction

An adverse reaction means any adverse event caused by FMT. Adverse reactions are a subset of all suspected adverse events for which there is reason to conclude that FMT caused the event.

5. Suspected Adverse Reaction

Suspected adverse reaction means any adverse event for which there is a reasonable possibility that FMT caused the adverse event. For the purposes of IND safety reporting, 'reasonable possibility' means there is evidence to suggest a causal relationship between FMT and the adverse event. A suspected adverse reaction implies a lesser degree of certainty about causality than adverse reaction, which means any adverse event caused by a therapy.

6. Unexpected

An adverse event or suspected adverse reaction is considered "unexpected" if it is not listed in the Investigator brochure or is not listed at the specificity or severity that has been observed; or is not consistent with the risk information described in the general investigational plan or elsewhere in the current application.

VI-B. Solicited Adverse Events

Short-term

The following short-term AEs and their associated intensities will be solicited:

- Fever
 - Mild 37.7-38.6°C

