 generalized way, such as, "How have you been feeling since your last
 visit?" Subsequent solicited questions and relevant details will be asked if
 there is a positive response. Site Investigators will be contacted by study
 representative if there is a suspected or reported AE
- Subjects having AEs will be monitored with relevant clinical assessments and laboratory tests, as determined by the site Investigator
- AEs, actions taken as a result of AEs, and follow-up results will be recorded as well as in the subject's source documentation. Follow-up laboratory results should be filed with the subject's source documentation
- Subjects will receive a follow-up phone call 6 and 12 months post-FMT to record any SAEs, new medical conditions/new medications, or changes in pre-existing medical conditions

VI-D. Assessment of Adverse Events

1. Assessment of Severity

The severity of AEs will be assessed according to the following definitions: •Mild: the AE is noticeable to the patient and/or the Investigator, but does not interfere with routine activity

•Moderate: the AE interferes with routine activity, but responds to symptomatic therapy or rest

•Severe: the AE significantly limits the patient's ability to perform routine activities despite symptomatic therapy

2. Assessment of Causality

The Investigator must assess the relationship of any AE (including SAEs) to FMT, as related or not related, based on clinical judgment and using all available information, and may include consideration of the following factors:

• Possible alternative causes of the AE, including the disease under treatment, pre-existing conditions, concomitant use of other drugs, and presence of environmental or genetic factors

- The temporal association between FMT exposure and onset of the AE
- Whether the manifestations of the AE are consistent with known actions or theoretical toxicity of FMT

The causal relationship between FMT and the AE will be assessed using one of the following categories:

Not Related: An AE is not associated with FMT if:

• Temporal relationship is lacking (e.g., the event did not occur within a reasonable time frame following administration of FMT); or

• Other causative factors more likely explain the event (e.g. pre-existing condition, other concomitant treatments);

Related: An AE is attributed to FMT if:

• There is a positive temporal relationship (e.g. the event occurred within a reasonable time frame following FMT); and

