• The AE is more likely explained by FMT than by another cause

VI-E. Reporting Safety Observations by the Investigator to the Sponsor

1. Reporting of Non-serious AEs

All AEs, regardless of seriousness, severity, or causal relationship to FMT, will be recorded in the AE section of the subject case report form.

2. Reporting of FMT Exposure during Pregnancy

If a female subject or the female partner of a male subject becomes pregnant during the course of study, the Investigator must report this occurrence to the Sponsor within **72 hours** of becoming aware of the pregnancy. The Investigator is required to follow up on the pregnancy until it has completed. The outcome of the pregnancy and the status of the newborn (if applicable) will be reported within 24 hours of becoming aware. If the female partner of a male subject becomes pregnant, the Investigator must obtain consent to collect pregnancy information (including the status of the newborn, if applicable).

3. Reporting of Safety Observations by the Investigator

Any occurrence of the following events or outcomes must be reported expeditiously by the Investigator or qualified designee to the local IRB and to the Sponsor, who will be responsible for reporting the event to the FDA:

- 1. SAE related to FMT material
- 2. Death of a subject related to FMT material

The site Investigator is to report any safety observations from the list above to the Sponsor within **72 hours** of becoming aware of the event, who in turn, will notify the FDA. Any observation that is also an AE will be recorded on the subjects case report form along with any actions taken. If not all information is available at the time of initial report, follow up SAE reports will be completed and submitted.

Any occurrence of the following events or outcomes must be reported by the Investigator or qualified designee to the local IRB and to the Sponsor, who will be responsible for reporting the event to the FDA:

- 1. SAE unrelated to FMT material
- 2. Death of subject unrelated to FMT material
- 3. Hospitalization related to CDI
- 4. New or worsening medical condition, or new medications

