A serious and unexpected adverse reaction is a SAE as determined by the Investigator or Sponsor, as defined previously, in combination with unexpected, defined as not being listed in the Investigator Brochure. At the request of the FDA, it will also include any documented infectious disease, defined as a new onset infection in the recipient after FMT and the infection present in the safety aliquot, which is a sample of the exact specimen that was transferred to the patient.

B. Findings from other sources

The Sponsor will also expeditiously report any findings from clinical, epidemiological, or pooled analysis of multiple studies or any findings that

suggest a significant risk in humans exposed to FMT and thought related to the material.

C. Increased occurrence of serious suspected adverse reactions related to FMT material

The Sponsor will report any clinically important increase in the rate of a serious suspected adverse reaction over that listed in the protocol.

VI-G. Halting Rules

Specific safety findings will result in temporarily suspending enrollment until a safety review is convened, the objective of which is to determine whether the study should continue per protocol, proceed with caution, be further investigated, be discontinued, or be modified and then proceed. Suspension of enrollment, for a particular group, such as colonoscopy group, or for the entire study, is another potential outcome of a safety review.

Subsequent review of serious, unexpected, and related AEs by the Data and Safety Monitoring Board (DSMB), IRB, the Sponsor, or the FDA or relevant local regulatory authorities may also result in suspension of further trial interventions/administration of FMT at a site. The FDA and study Sponsor(s) retain the authority to suspend additional enrollment and study interventions/administration of FMT for the entire study, as applicable.

Findings that will trigger a safety review are

- Death related to FMT material
- Confirmed transmission of a clinically concerning infection from donor to subject via FMT
- If one or more subjects experiences a serious, unexpected adverse event related to FMT material
- Significant increase in frequency of events theoretically related to FMT material (specifically, new diagnoses of inflammatory bowel disease). Discussion on threshold will be discussed with DSMB and will be on a disease specific basis.

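### VI-D.2 codes a serious event Not Related whenever another cause is likelier, so a suspected reaction under VI-A.5 can go to the sponsor on the 7-day rather than the 72-hour clock

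*Combined protocol and SAP*

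**What the plan says.** All sections cited are in part 6 of the combined document (Protocol).

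- **VI-D.2, causality.** The choice is binary: "The Investigator must assess the relationship of any AE (including SAEs) to FMT, as related or not related". Not Related applies if the timing does not fit, or if this holds: "Other causative factors more likely explain the event". Related needs fitting timing and also this: "The AE is more likely explained by FMT than by another cause".
- **VI-A.5, suspected adverse reaction.** This is "any adverse event for which there is a reasonable possibility that FMT caused the adverse event". Reasonable possibility in turn "means there is evidence to suggest a causal relationship between FMT and the adverse event". The section gives that meaning with a stated scope: "For the purposes of IND safety reporting". It adds that a suspected reaction is less certain than an adverse reaction.
- **VI-E.3, investigator reports.** SAEs and deaths related to FMT material go to the sponsor within 72 hours. The 7-day list includes "SAE unrelated to FMT material" and unrelated deaths. Both lists also go to the local IRB.
- **VI-F, sponsor reports to the FDA.** The IND safety-report criteria refer to suspected adverse reactions related to FMT material.
- **VI-G, halting rules.** Four findings trigger a safety review with enrolment suspended. The first is "Death related to FMT material"; the third is a serious, unexpected event related to FMT material. The other two are proven donor-to-recipient infection and a rise in theoretically related diagnoses. Separately, an SAE related to FMT bars that subject from a second FMT.

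**The concern.** The protocol holds two standards of causality, and nothing in it connects them. The lower one (VI-A.5) recognises that a serious event may deserve attention when FMT is a credible cause but not the likeliest. The higher one (VI-D.2) is the only rule for coding an event, and the investigator's reporting clock depends on the result.

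This matters more here than in a controlled trial. Safety is the main objective, there is no untreated arm, and section X says excess risk over baseline will be hard to discern, so prompt review of individual cases carries more of the load. Section X also expects an older cohort with comorbidities, and VI-D.2 names pre-existing conditions and concomitant treatments as examples of alternative causes. A likelier alternative will often be available. Uncertain attribution is foreseeable: VII-B describes two earlier bacteremia cases whose link to FMT could not be settled.

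VI-D.2 also asks only about FMT as a whole, whereas the 72-hour rule and the first and third VI-G triggers act on FMT material. Section VI separates procedure-related from material-related events, but the VI-D.2 code does not.

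**Working it through.** No sample size or error rate is involved. The check takes a serious event through each definition, then through each rule that uses the result.

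**Step 1. The two standards side by side** (an SAE with fitting timing)

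| Investigator's judgment | VI-D.2 code | Suspected reaction under VI-A.5? |
|---|---|---|
| FMT likelier than any other cause | Related | Yes |
| FMT and another cause equally likely, with evidence for FMT | Neither definition fits | Yes |
| Another cause likelier, with evidence for FMT | Not Related | Yes |
| Another cause likelier, no evidence for FMT | Not Related | No |

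The gap is the third row. The second row is a hole in the definitions: Related and Not Related each require one cause to be likelier.

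**Step 2. The reporting clock (VI-E.3)**

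Inputs: 72 hours for a related SAE, 7 days for an unrelated one. The investigator both codes the event and sends the report, so the code leads directly to the clock.

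- 7 days × 24 = 168 hours
- 168 − 72 = 96 hours = 4 days

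A third-row SAE has a deadline 96 hours later than a first-row SAE.

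**Step 3. The VI-G rules, conditional on the VI-D.2 code deciding relatedness there**

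Two of the four triggers require relatedness, but what a given SAE could miss depends on its type:

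| Third-row SAE | Trigger 1 (related death) | Trigger 3 (serious, unexpected, related) | Second-FMT bar |
|---|---|---|---|
| Fatal | Missed | Missed if unexpected | Moot |
| Non-fatal, unexpected | Not applicable | Missed | Missed |
| Non-fatal, expected | Not applicable | Not applicable | Missed |

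The bar has practical effect only for a subject with clinical non-response who needs vancomycin or fidaxomicin within 6 weeks, opts for a second FMT, and has a physician who agrees.

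**Step 4. The same SAE with VI-A.5 wording in VI-D.2**

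It would be Related and on the 72-hour clock, 96 hours earlier.

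**The case against.** The strongest reply is that two thresholds need not conflict. VI-A.5 limits its meaning to IND safety reporting, and VI-F uses the matching term. VI-D.2 is the investigator's clinical attribution, and a sponsor may choose to reserve automatic suspension of enrolment for events more likely than not due to FMT. This stands for VI-G and for the second-FMT bar: a lower threshold there has a real cost in a comorbid cohort where one serious, unexpected, related event suspends enrolment. It does not explain why the investigator's early report should wait, since the sponsor needs that report to judge whether an event is a suspected reaction. Nor does it give the equally likely event a code.

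It is also fair that VI-G does not say who decides relatedness. It names the DSMB, IRB, sponsor and FDA as reviewers of related events, so a missed trigger is conditional.

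Safeguards remain. Unrelated SAEs still go to the local IRB and the sponsor, the sponsor reviews the whole safety database, the DSMB meets quarterly and can convene over any adverse event, the sponsor and FDA can suspend enrolment, and a second FMT via colonoscopy is at the physician's discretion. Infections have further routes that do not depend on VI-D.2: the proven-transmission trigger, and IND reporting when the infection is also found in the retained donor aliquot.

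A reader might infer four stronger points that the documents do not support:

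- **That one SAE loses every protection.** Step 3 shows it cannot: a death makes the bar moot, and a non-fatal event could never meet trigger 1.
- **That FDA notification is delayed.** VI-F may already run on the VI-A.5 standard. VII-E restates the 15- and 7-day duties without the word suspected, which makes the wording unclear but does not establish a delay.
- **That SAEs drop out of the safety results.** Data Analysis reports raw events and crude rates for the whole cohort. No related-only analysis is stated, so any effect on the SA1 and SA2 hypotheses is inference.
- **That the summary table in part 9, III-D gives a rate.** Its possibly related entries are AEs, not SAEs, in immunocompromised patients whom this study largely excludes.

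**Conclusion.** The concern holds in limited form. An SAE can be a suspected adverse reaction under VI-A.5 and Not Related under VI-D.2, and equally likely causes have no code. The firm consequence is an investigator deadline 96 hours later. This rests on VI-D.2 being the rule the investigator applies in VI-E.3; the protocol gives no other.

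The second consequence is conditional. If the VI-D.2 code also decides relatedness in VI-G, such an SAE would not by itself open a safety review (trigger 1 if fatal, trigger 3 if unexpected) or, if non-fatal, bar a second FMT. What is lost is automatic action; review by judgment remains.

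The number of affected SAEs is unknown, and nothing in the documents allows an estimate.

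**What to change.** 1. In VI-D.2, either define Related as a reasonable possibility in the VI-A.5 sense and Not Related as the absence of such evidence, or keep the present codes and add a possibly related level that also covers equally likely causes.
2. In VI-E.3, apply the 72-hour report to these SAEs.
3. Record attribution to FMT material and to the delivery procedure as separate items.
4. In VI-G and for the second-FMT bar, state who decides relatedness, and send possibly related SAEs promptly to the DSMB or sponsor for a decision. Whether they should suspend enrolment or bar retreatment automatically is a trade-off for the sponsor and DSMB. If the first option in item 1 is chosen, VI-G needs its own stated threshold; otherwise the lower standard carries into the automatic rules by default.

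The cost is two definitions or one added level, one attribution item, short wording changes in VI-E.3 and VI-G, and a check that the Appendix 4 forms match. In conduct, expect some additional 72-hour reports and case reviews. The VI-A.5 requirement for evidence of causation limits their number.

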The Investigator is to report any safety observations from the list above to the Sponsor within **7 days** of becoming aware of the event. The Sponsor will notify the FDA in its Annual Report. Any observation that is also an AE will be recorded on the subjects case report form along with any actions taken. If not all information is available at the time of initial report, follow up SAE reports will be completed and submitted.

The site Investigator is required to follow SAEs until resolution, regardless of whether the subjects are still participating in the study. Resolution is defined as:

- Resolved with or without residual effects
- Return to baseline for a pre-existing condition
- Fatal outcome; if autopsy is performed, the autopsy report must be provided to the Sponsor.

VI-F. Monitoring the study database and submitting safety reports

The Sponsor will notify FDA of any unexpected fatal or life-threatening suspected adverse reaction related to FMT material as soon as possible, but no later than 7 calendar days after the Sponsor's initial receipt of the information. The Sponsor will notify the FDA and all participating Investigators in an IND safety report of potentially serious risks from this study as soon as possible, but no later than 15 calendar days after the Sponsor receives the safety information and determines that the information qualifies for reporting. Participating Investigators include all Investigators enrolling subjects under the Sponsor's IND. In addition, the Sponsor will identify in each IND safety report, all IND safety reports previously submitted to FDA concerning a similar suspected adverse reaction and will analyze the significance of the suspected adverse reaction in light of previous, similar reports or any other relevant information. The Sponsor will evaluate a suspected adverse reaction in the context of other related reports or adverse events. The Sponsor will periodically review and analyze the entire safety database, for IND safety reporting purposes, and also to update Investigator brochures with new safety information. An IND safety report will be submitted when any of the following criteria are met:

A. Serious and unexpected suspected adverse reaction related to FMT material

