There have been no confirmed infectious complications directly attributable to FMT reported in the literature to date aside from a speculation about a norovirus case although the donor was untested for this.²⁹ There have been two FMT cases of bacteremia, although the strength of the association is unclear, and both patients did well on antibiotic therapy. However, since the process involves infusion of one person's "body fluids" into another person, transmission of an infectious agent or other disease or condition remains a theoretical possibility. From infusion of donor microbiome, the patient/subject could potentially acquire risk factors for chronic diseases such as diabetes or inflammatory bowel disease. Risks will be minimized by a rigorous donor selection process and evaluative studies on stool and blood of the donor to exclude transmission of infectious agents prior to FMT. Subjects will be informed that the treatment or procedure may involve these theoretical risks and additional risks that are currently unforeseeable. There have been reported cases of inflammatory bowel disease flares post-FMT, but it is unclear if this was attributable, and these patients have been excluded from this study. Infusion of fecal material containing a potential agent to which the subject is allergic is also a concern and so patients with a history of severe (anaphylactic) food allergy will be excluded from this study.

VII-C. Potential Risks to Donors

This study also involves individuals (donors) recruited to donate stool for FMT. There are 3 areas of risk to the potential stool donor.

These include:

 Physical risks related to laboratory testing and the stool collection protocol
 Psychological risks related to both revealing and potentially learning sensitive information during donor screening process

3) Risks related to confidentiality and loss of privacy.

OpenBiome volunteer donors will be utilized. In order to exclude donors at high risk of passing infection, a Donor Risk Factor Questionnaire (*Appendix* 2) will be administered. This questionnaire contains sensitive and potentially embarrassing questions

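### Section VI-F.A restates *unexpected* as Brochure listing alone, contradicting VI-A.6, so a listed but worse-than-listed related SAE can miss the formal 15-day IND safety report

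*Combined protocol and SAP*

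**What the plan says.** Section VI-A (Adverse Events Reporting, Definitions), item 6, makes an event or suspected reaction unexpected if it is "not listed in the Investigator brochure or is not listed at the specificity or severity that has been observed", or if it "is not consistent with the risk information described in the general investigational plan or elsewhere in the current application".

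Section VI-F sets the Sponsor's reporting duties. Its opening paragraph requires FDA notice within 7 calendar days for an unexpected fatal or life-threatening suspected reaction related to FMT material. It also requires an IND safety report, to the FDA and all participating Investigators, within 15 calendar days of the Sponsor receiving the information and judging it reportable. It then states: "An IND safety report will be submitted when any of the following criteria are met". Criterion A is a serious and unexpected suspected reaction related to FMT material. It describes this as an SAE as previously defined, "in combination with unexpected, defined as not being listed in the Investigator Brochure". A further sentence adds, at FDA request, new infections also found in the safety aliquot.

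Section VI-G lists four findings that prompt a safety review. The third reads: "If one or more subjects experiences a serious, unexpected adverse event related to FMT material". VI-G gives no definition of *unexpected*.

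**The concern.** The two sections give one word two meanings, and criterion A depends on that word. Under VI-A.6 an event already in the Brochure can still be unexpected, because it "is not listed at the specificity or severity that has been observed" or because it conflicts with other risk information. Under VI-F.A, once a term is listed, every later occurrence counts as expected, however severe.

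What can be lost is the formal report on such an event: its 15-day limit and its circulation to every participating Investigator. This matters because safety is the study's overarching objective and, as section X concedes, there is no untreated arm. Careful handling of single cases therefore carries much of the weight. VI-F also plans to update the Brochure with new safety information. Under the Brochure-only wording, each newly listed term removes that term from criterion A at any severity. Under VI-A.6 it does so only up to the severity and specificity listed.

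**Working it through.** No figure in the plan bears on this, so the check compares the two definitions and then traces one event through each rule.

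**Step 1. The definitions, ground by ground.**

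| Ground for *unexpected* | VI-A.6 | VI-F.A |
|---|---|---|
| Not listed in the Brochure | yes | yes |
| Listed, but not at the observed specificity or severity | yes | absent |
| Inconsistent with the plan's or application's risk information | yes | absent |

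VI-F.A keeps 1 of 3 grounds. It cannot easily be read as shorthand for VI-A.6. In its sentence the pointer to an earlier definition attaches to the SAE, while *unexpected* receives a separate, explicit meaning.

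**Step 2. A test event.** Take an SAE that is related to FMT material, neither fatal nor life-threatening, and listed in the Brochure at a lesser severity than observed. As an illustration, the opening list of section VI names allergic reaction as a material-related event. Assume the Brochure lists it only in a mild form, and a subject is admitted for more than 24 hours with a worse but not life-threatening reaction.

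**Step 3. The event under each rule.**

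| Rule | Result |
|---|---|
| VI-A.6 | Unexpected, on the severity ground |
| VI-F criterion A, as worded | Not unexpected, because listed; not met |
| VI-F.A safety-aliquot sentence | Applies only to a new infection also found in the aliquot; not met |
| VI-F criterion B | Headed as findings from other sources; its broad wording might catch some cases |
| VI-F criterion C | Concerns a raised rate; a single more severe case does not meet it |
| VI-E, item 3 | Met: to the local IRB, to the Sponsor within 72 hours, then to the FDA, whether or not expected |
| VI-F 7-day notice | Not reached, because the event is not life-threatening |
| VI-G third trigger | Met if VI-A.6 governs, which is the natural reading |
| VII-E | Uncertain: it turns on *unanticipated*, which is not defined |

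**Step 4. What is left uncovered.** The event is unexpected in VI-A.6 and expected in VI-F.A. VI-E brings it to the FDA, but sets no time limit for the Sponsor's step and does not require notice to Investigators at other sites. VII-E promises FDA reports in 15 days for *unanticipated* serious related events, but sends anticipated and less serious ones in annually. A reader who equates listed with anticipated would gain nothing from the 15-day promise.

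**The case against.** The strongest reply is that the mismatch is one of wording and the safeguards around it are substantial. Much of that stands.

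- **The FDA is told.** VI-E does not depend on expectedness. All AEs go on the case report form, SAEs are a study endpoint, and the DSMB meets quarterly and can convene in between. A reader might infer that worse-than-known harm is filtered out of the study. The documents do not support that; only the formal IND safety report is at risk.
- **The 7-day notice.** A reader might infer that this is lost too. It sits in VI-F's opening paragraph, outside criterion A, and uses *unexpected* without redefining it. VI-A is the Definitions section, so VI-A.6 most naturally applies.
- **The halting rule.** A reader might infer that the third VI-G trigger would not fire. The same reasoning applies: the narrow wording is not in VI-G, so the effect is at most an ambiguity. "Death related to FMT material" and confirmed transmission of a clinically concerning infection prompt review without reference to expectedness, and the FDA and the Sponsor keep authority to suspend.
- **Disagreement between sites.** Sites must report every material-related SAE whether or not it is expected, and the Sponsor submits the IND safety reports. Inconsistent classification by sites is not an evident consequence.
- **Infection as an example.** Section VII-B says: "There have been two FMT cases of bacteremia, although the strength of the association is unclear". One might build a case of septic shock after listed bacteremia. It is a poor test. Septic shock would ordinarily be life-threatening and so within the 7-day duty. The follow-up data items name sepsis and bacteremia separately, so listing one need not list the other. The safety-aliquot sentence may also catch the event.

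These points narrow the consequence. They do not reconcile VI-F.A with VI-A.6, and none of them supplies the 15-day notice to all participating Investigators for the test event.

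**Conclusion.** The contradiction is certain and is in current text: VI-F.A drops two of the three grounds in VI-A.6. Its clear consequence is limited to criterion A. For a material-related SAE that is listed but worse, or more specific, than listed, a literal reading allows the 15-day IND safety report and its circulation to all participating Investigators to be omitted. The FDA would still be notified under VI-E, with no stated deadline for the Sponsor. Criteria B and C and the safety-aliquot sentence would catch some such cases.

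Any effect on the 7-day notice or the third halting trigger is only a possible ambiguity, since both most naturally follow VI-A.6.

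The conclusion about the wording rests on no assumption. The practical size cannot be stated: the Brochure is not in the material reviewed, so the listed terms and severities are unknown and no actual event can be shown to fall in the gap. The allergic-reaction case is an illustration on an assumed listing.

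**What to change.** In VI-F.A, delete the Brochure-only definition and refer instead to *unexpected* as defined in VI-A.6. Then reconcile the other places that rely on the idea. The 7-day notice in VI-F and the third trigger in VI-G should each state which definition applies. VII-E should either define *unanticipated* or replace it with the defined term.

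The cost is one sentence and a few cross-references in a protocol amendment. The downside is possibly a few more expedited reports.
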